5.3. SAFETY DATA

All the safety analyses will be done on the Safety set.

Adverse events

The incidence of Adverse Events (AEs) recorded through Day 5 and Serious Adverse Events (SAEs) recorded through Day 14 will be presented for the Safety set. Treatment emergent AEs/SAEs will be considered as those AEs/SAEs with an onset date and time after treatment initiation for the serelaxin group. For the Standard of Care Only group, date and time of randomization will be considered as treatment initiation. In case of missing time of onset of the event, only the onset date will be used for the evaluation of the incidence of the AE. Adverse events with an onset between informed consent and treatment initiation will be listed separately.

Tables reporting general summary of AEs will be produced by treatment group specifying the number of total events and absolute and relative frequency of patients with AEs. As a patient may have more than one AE, the total number of AEs could be greater than the total number of patients. Further summaries by treatment group will be produced for non-serious AE and serious AE by time period, e.g., through Day 5 and through Day 14.

Absolute and relative frequency of patients with drug-related AEs, severe AEs, SAEs, AEs with an outcome of death, AEs leading to permanent discontinuation of treatment, AEs indicative of safety risk and events of interest (please refer to the section below for the definition of safety risk events and events of interest) will also be reported for treatment emergent AEs. The number of distinct adverse events by low level term will be provided. Drug-related AEs will be the AEs with relationship to study treatment equal to “Yes”, “Yes, investigational treatment”, “Yes, other study treatment (not-investigational)”, “Yes, both and/or indistinguishable”; if the

	Statistical Analysis Plan
	Sponsor: NOVARTIS Protocol number: CRLX030A3301

relationship to study drug is unknown or missing, the AE will be considered to be drug-related as well. eCRF severe events will be considered as severe events in the analysis. These summaries will be repeated for treatment emergent SAEs.

Treatment emergent AEs will be tabulated by System Organ Class (SOC) and Preferred Term (sorted in alphabetical order within each SOC) using the latest MedDRA dictionary, and by System Organ Class, Preferred Term and severity. Absolute and relative frequency of patients who have experienced each type of event will be presented; if the same patient reported more than one occurrence of the same AE with different intensity, the worst reported severity grade for each event for the patient will be used for the analysis. The most frequent treatment emergent AEs will also be tabulated by Preferred Term sorted by descending frequency for AEs with an incidence rate of at least 5% in the serelaxin group.

In addition, treatment emergent adverse events associated with

- worsening heart failure (WHF)/all cause death through Day 5
- confirmed systolic blood pressure decrease event (CBPDE)

will be summarized by system organ class and preferred term. These AEs are determined by taking the answer “Yes” to the questions “Does AE meet the definition of Endpoint?” and “Does AE meet the definition of Systolic Blood Pressure Decrease Event?”, respectively.

Treatment emergent SAEs will be summarized similarly. Treatment emergent SAEs will be summarized by time period of onset, i.e., through Day 5 and through Day 14. Treatment emergent SAEs are defined as those which start after treatment start for serelaxin group, or after randomization for Standard of Care group.

All study-drug-related AEs, AEs with an outcome of death, AEs leading to permanent discontinuation of treatment will be listed with all their details. Time from the treatment start for serelaxin group or from randomization for Standard of Care group, to the AE start/end date, will be also computed. Elapsed days, hours and minutes plus 1 minute will be reported on the listing.

In case of an ongoing event, no days relative to the end of the event will be computed.

In case of missing time of start or end of an event, no relative days will be computed.

Safety risks and events of interest

Adverse events will be also presented according to the search strategies using the latest MedDRA dictionary version available before database lock, as specified in the Case Retrieval Strategy (CRS) defined by Novartis. Adverse events will be characterized as safety risks and as events of interest according to the rules specified in Table 5.3-1 and Table 5.3-2, respectively.

Safety risks and events of interest through Day 5 and Day 14 will be summarized by treatment group and tabulated by safety risk / events of interest, NMQ, HLGT, SMQ or SOC, and Preferred Term of MedDRA dictionary. Absolute and relative frequency of patients who have experienced each type of event will be presented.

	Statistical Analysis Plan
	Sponsor: NOVARTIS
	Protocol number: CRLX030A3301

Table 5.3-1: MedDRA* search specifications to evaluate safety risks

Safety Risk	Specification
Hypotension (identified)	NMQ 'Hypotension' (Broad) CMQ ' Hemoglobin/ hematocrit transient decrease '
Hemoglobin/ hematocrit transient decrease (potential)	
 • SMQ 'Haemorrhages' (Broad) • HLGT 'Anaemias nonhaemolytic and marrow depression' • SMQ 'Haematopoietic erythropenia' (Broad)
Fetotoxicity and teratogenicity (potential)	SMQ 'Pregnancy and neonatal topics' (Broad)

CMQ: Customized MedDRA query; HLGT: High level group term; NMQ: Novartis MedDRA query; SMQ: Standardized MedDRA query.

* According to MedDRA v19.1. Specifications could possibly change before database lock.

	Statistical Analysis Plan
	Sponsor: NOVARTIS
	Protocol number: CRLX030A3301

Table 5.3-2: MedDRA* search specifications to evaluate events of interest

Event of Interest	Specification
Menorrhagia/Metrorrhagia	HLGT 'Menstrual cycle and uterine bleeding disorders'
Hypokalemia	NMQ 'Hypokalemia' (Broad)
Hypersensitivity/Immunogenicity	CMQ ' Hypersensitivity, Immunogenicity, Cutaneous reactions ': 
 • SMQ 'Hypersensitivity' (Broad) • SMQ 'Angioedema' (Broad) • SMQ 'Anaphylactic reaction' (Broad) • SOC 'Immune system disorders' • HLGT 'Immunology and allergy investigations' • HLGT 'Administration site reactions' • SMQ 'Severe cutaneous adverse reactions' (Broad)
Cardiac failure	SMQ 'Cardiac failure' (Broad) CMQ ' Cardiac arrhythmias/QT prolongation ': 
 • SMQ 'Torsade de pointes/QT prolongation' (Broad) • SMQ 'Cardiac arrhythmias' (Broad)
QT prolongation	
Thromboembolic events	SMQ 'Emolic and thrombotic events' (Broad) CMQ ' Renal impairment ': 
 • SMQ 'Acute renal failure' (Broad) • PT 'Chronic kidney disease'
Renal impairment	
Respiratory failure	SMQ 'Respiratory failure' (Broad)
Hepatotoxicity	SMQ 'Drug related hepatic disorders – comprehensive search' (Broad)
Potential promotion of cancers	SMQ 'Malignancies' (Broad)

CMQ: Customized MedDRA query; HLGT: High level group term; NMQ: Novartis MedDRA query; SMQ: Standardized MedDRA query; SOC: System organ class.

* According to MedDRA v19.1. Specifications could possibly change before database lock.

Liver events

Liver events are a subgroup of Adverse Events.

As a patient may have more than one liver event the total number of liver events could be greater than the total number of patients. The number of subjects with 0, 1, 2, >2 liver events will be summarized by treatment. Summary statistics on data about liver events will be provided by treatment.

Liver events details, collected in the "Liver Event - Overview" section and including medical history possibly contributing to liver dysfunction, alcohol consumption, drug abuse and acetaminophen/paracetamol intake, will be described presenting absolute and relative frequencies of liver events in each category of variable (percentages will be calculated on the total of liver events with non-missing information).

	<h2 style="margin: 0;">Statistical Analysis Plan</h2>
	Sponsor: NOVARTIS Protocol number: CRLX030A3301

Imaging, pathology, autoimmune and viral serology assessments will be presented with the total of liver events; results will be presented by each procedure and percentages will be calculated on each procedure with non-missing information.

Vital signs

Vital signs evaluations will include measurements of body weight (Kilogram), body mass index (kg/m^2), height (cm) at screening, body temperature (Celsius), respiratory rate (Breath/min), pulse (Beats/min) and systolic and diastolic blood pressure (mmHg). Conversions from different units will be performed as aforementioned (see Section 5.1).

Summary statistics (i.e., number of observations, mean, standard deviation, median, first and third quartiles, minimum and maximum) of raw data and change (absolute and %) from screening (i.e., start of screening for all parameters and end of screening only for pulse and blood pressure) will be provided at each assessment time point. Treatment groups will be compared for changes (absolute) from screening (i.e., start and end, where applicable) for each parameter. The estimated difference between treatment groups and 95% CI will be presented.

For serelaxin group only, descriptive statistics of raw data and change (absolute and %) versus the pre-dose value will also be provided for heart rate (Beats/min) and systolic and diastolic blood pressure (mmHg) collected for drug infusion and post-drug infusion monitoring.

Summary statistics for raw data, absolute change and percentage change from screening, and absolute change and percentage change from Day 5 will be provided by treatment group for heart rate (Beats/min), systolic and diastolic blood pressure (mmHg) collected daily through the hospitalization (after Day 5 and up to Day 29).

Line plots of the mean and standard error of systolic and diastolic blood pressure over time by treatment group will be provided.

Laboratory data: hematology and chemistry

Summary statistics of raw data and change (absolute and %) from screening at each scheduled visit and for each laboratory parameter will be presented by treatment group. Laboratory data will be analysed and presented considering the preferred unit of measurement. Treatment groups will be compared for changes (absolute) from screening for each parameter. The estimated difference between treatment groups and 95% CI will be presented.

Laboratory data will also be summarized by presenting for each laboratory parameter shift tables showing the pattern of change from screening versus each post-screening visit, based on the cross-classification of the number and percentage of subjects in each treatment group with any post-screening value that is below [low], within [normal], above [high], below&above [low&high] the normal ranges.

Abnormal laboratory values will be presented for each subject in a data listing with an indication of whether the value is above (H) or below (L) the normal reference range and if it is notable.

	<h2>Statistical Analysis Plan</h2>
	
Sponsor: NOVARTIS

Protocol number: CRLX030A3301

The categorical analysis for laboratory parameters will be presented using the criteria reported in Table 5.3-3. The number and percentage of subjects meeting each specified criterion will be tabulated by visit and for any post-baseline visit. For those criteria with the specified cut off point (e.g., < or > x.x), the summary statistics will be presented for baseline and each post-baseline visit, with the denominator including those subjects with evaluable measurements at the specified visits. For criteria with specification regarding the relative change from baseline, the summary statistics will be presented for each post-baseline visit with the denominator including those subjects with evaluable measurements at both baseline and the corresponding post-baseline visit.

Statistical Analysis Plan

Sponsor: NOVARTIS

Protocol number: CRLX030A3301

Table 5.3-3: Categorical analysis for laboratory parameters

	Parameter categories	Criterion
Hematology	Red blood cell counts (RBC)	>50% increase >20% decrease $<2.5 \times 10^6/\mu\text{L}$ $>8.5 \times 10^6/\mu\text{L}$
	Hemoglobin	>50% increase >20% decrease $>20 \text{ g/dL}$ $<8 \text{ g/dL}$
	Hematocrit	>50% increase >20% decrease $<20\%$ $>60\%$
	RBC, Hemoglobin, & Hematocrit	RBC > 20% decrease AND Hemoglobin > 20% decrease AND Hematocrit > 20% decrease
	White blood cell counts (WBC)	>100% increase >50% decrease $<3.5 \times 10^9/\text{L}$ $>25 \times 10^9/\text{L}$
	Platelet	>75% increase >50% decrease $<50 \times 10^9/\text{UL}$ $>600 \times 10^9/\text{UL}$
	Neutrophils	$<1.5 \times 10^9/\text{L}$ $<1.0 \times 10^9/\text{L}$
	Lymphocytes	None
Serum Chemistry	Blood Urea Nitrogen (BUN)	>100% increase $>14.28 \text{ mmol/L}$
	Creatinine	>100% increase >50% increase Increase of $\geq 0.3 \text{ mg/dL}$ Increase of $\geq 0.5 \text{ mg/dL}$ Increase of $\geq 1.0 \text{ mg/dL}$ $>2 \text{ mg/dL}$ $>2.5 \text{ mg/dL}$
	Estimated Glomerular Filtration Rate (eGFR)	Decrease of >25% Decrease of >50% Decrease of $>30 \text{ mL/min}/1.73\text{m}^2$
	Potassium	$>6 \text{ mmol/L}$ $>5.5 \text{ mmol/L}$ $<3.0 \text{ mmol/L}$
	Calcium	$<1.75 \text{ mmol/L}$ $>3.1 \text{ mmol/L}$
	Sodium	$<120 \text{ mmol/L}$ $<130 \text{ mmol/L}$ $>155 \text{ mmol/L}$

Statistical Analysis Plan

Sponsor: NOVARTIS

Protocol number: CRLX030A3301

In addition, for the liver function test (LFT), summary table will be provided on the number and proportion of patients having the criteria defined in Table 5.3-4. These are evaluated at each post-baseline visit as well as at any post-baseline visit. The data are summarized using two approaches:

1. Patients with newly occurring abnormalities, defined as events occurring post baseline for patients who did not meet the abnormal criteria at baseline (Table 5.3-4).
2. Patients with abnormalities post baseline, regardless of the baseline values (Table 5.3-5).

Table 5.3-4: LFT categorical analysis ('newly occurring')

Category family	Category - Numerator Subjects at risk meeting the criteria at post BL	Denominator Subjects at risk and meeting the following criteria at BL
ALT/AST	ALT or AST >3x ULN ALT or AST >5x ULN ALT or AST >8x ULN ALT or AST >10x ULN	Subjects with ALT and AST ≤3x ULN at BL
Hy's chemistry category	ALT or AST >3x ULN and TBL >1.5x ULN ALT or AST >3x ULN and TBL >2x ULN ALT or AST >5x ULN and TBL >2x ULN ALT or AST >8x ULN and TBL >2x ULN ALT or AST >10x ULN and TBL >2x ULN ALT or AST >3xULN and TBL >2x ULN and ALP <2x ULN	Subjects with ALT and AST ≤3x ULN at BL
TBL & ALP	TBL >1.5x ULN and ALP >2x ULN TBL >2x ULN and ALP >2x ULN	Subjects with TBL ≤1.5x ULN and ALP ≤2x ULN at BL (comment: the intention is that both parameters must be below threshold)
Isolated TBL	TBL >1.5x ULN & ALT and AST ≤3x ULN and ALP ≤2x ULN TBL >2x ULN & ALT and AST ≤3x ULN and ALP ≤2x ULN TBL >3x ULN & ALT and AST ≤3x ULN and ALP ≤2x ULN	Subjects with TBL ≤1.5x ULN & ALT and AST ≤3x ULN and ALP ≤2x ULN (comment: same denominator as for 'isolated ALP')
Isolated ALP	ALP >2x ULN & ALT and AST ≤3x ULN and TBL ≤1.5x ULN ALP >3x ULN & ALT and AST ≤3x ULN and TBL ≤1.5x ULN ALP >5x ULN & ALT and AST ≤3x ULN and TBL ≤1.5x ULN	Subjects with ALP ≤2x ULN & ALT and AST ≤3x ULN and TBL ≤1.5x ULN (comment: same denominator as for 'isolated TBL')

ALP: alkaline phosphatase; ALT: alanine aminotransferase; AST: aspartate aminotransferase; TBL: total bilirubin; ULN: upper limit of normal.

	Statistical Analysis Plan
	Sponsor: NOVARTIS
	Protocol number: CRLX030A3301

Table 5.3-5: LFT categorical analysis ('any post-baseline elevation')

Category family	Category - Numerator Subjects at risk meeting the criteria at post BL	Denominator Subjects at risk
ALT/AST	ALT or AST >3x ULN	
	ALT or AST >5x ULN	
	ALT or AST >8x ULN	
	ALT or AST >10x ULN	
Hy's chemistry category	ALT or AST >3x ULN and TBL >1.5x ULN	
	ALT or AST >3x ULN and TBL >2x ULN	
	ALT or AST >5x ULN and TBL >2x ULN	
	ALT or AST >8x ULN and TBL >2x ULN	
TBL & ALP	ALT or AST >10x ULN and TBL >2x ULN	
	ALT or AST >3x ULN and TBL >2x ULN and ALP <2x ULN	Subjects with a post BL value
	TBL >1.5x ULN and ALP >2x ULN	
	TBL >2x ULN and ALP >2x ULN	
Isolated TBL	TBL >1.5x ULN & ALT and AST ≤3x ULN and ALP≤2x ULN	
	TBL >2x ULN & ALT and AST ≤3x ULN and ALP ≤2x ULN	
	TBL >3x ULN & ALT and AST ≤3x ULN and ALP ≤2x ULN	
Isolated ALP	ALP >2x ULN & ALT and AST ≤3x ULN and TBL ≤1.5x ULN	
	ALP >3x ULN & ALT and AST ≤3x ULN and TBL ≤1.5x ULN	
	ALP >5x ULN & ALT and AST ≤3x ULN and TBL ≤1.5x ULN	

Plots showing the relationship between maximum TBL and ALT or AST at any visit (eDISH plot for the evaluation of drug-induced serious hepatotoxicity) will also be provided.

Laboratory data: urinalysis

Summary statistics for data about urinalysis will be provided at each assessment time point by treatment group. For each parameter result, absolute and relative frequencies of patients reporting it will be provided. Percentages will be computed considering patients with non-missing information at each assessment time point.

Electrocardiogram (ECG)

The number and proportion of patients by procedure performed and overall interpretation will be provided at each assessment time point by treatment group. Percentages will be computed considering patients with non-missing information at each assessment time point. Summary statistics will be provided at each assessment time point by treatment group.

Heart rate (beats/min), mean PR duration (msec), mean QT duration (msec), corrected QT Fridericia interval (QTcF) and mean QRS duration (msec) will be described, providing number of observations, mean, standard deviation, median, first and third quartiles, minimum and maximum at each assessment time point by treatment group.

The number and proportion of patients with the following criteria at any post-baseline visit will be presented:

	Statistical Analysis Plan
	Sponsor: NOVARTIS
	Protocol number: CRLX030A3301

Table 5.3-6: Criteria for ECG categorical analysis

Topic	Parameter categories	Criterion for denominator
QT/QTcF	QT/QTcF >450 msec	Subjects with QT/QTcF ≤450 msec at BL
	QT/QTcF >480 msec	Subjects with QT/QTcF ≤480 msec at BL
	QT/QTcF >500 msec	Subjects with QT/QTcF ≤500 msec at BL
	QT/QTcF >450 msec; males only	Male subjects with QT/QTcF ≤450 msec at BL
	QT/QTcF >460 msec; females only	Female subjects with QT/QTcF ≤460 msec at BL
	QT/QTcF increase from BL >30 msec	Subjects with a non-missing value at BL and post BL
	QT/QTcF increase from BL >60 msec	Subjects with a non-missing value at BL and post BL
PR	PR >200 msec	Subjects with PR ≤200 msec at BL
	PR >220 msec	Subjects with PR ≤220 msec at BL
	PR > 200 msec and change from BL ≥25%	Subjects with PR ≤200 msec at BL
QRS	QRS >110 msec and change from BL ≥25%	Subjects with QRS ≤110 msec at BL
	QRS >120 msec and change from BL ≥25%	Subjects with QRS ≤120 msec at BL
Heart Rate	Heart rate >100 bpm and change from BL ≥25%	Subjects with heart rate ≤100 bpm at BL
	Heart rate <50 bpm and change from BL ≥25%	Subjects with heart rate ≥50 bpm at BL

In addition, shift tables comparing baseline ECG overall interpretation (normal, clinically insignificant abnormality, clinically significant abnormality) with Day 5/discharge ECG overall interpretation (normal, clinically insignificant abnormality, clinically significant abnormality) will be provided by treatment group.

A listing of clinically significant abnormalities in ECG evaluations will be provided.

Echocardiography

Echocardiography is not considered as study related procedures and is performed according to local diagnostic practice.

Overall interpretation will be described by providing the number and proportion of subjects in each category at each assessment time point by treatment group. Percentages will be computed considering patients with non-missing information at each assessment time point.

LV Ejection Fraction (%) will be described by means of summary statistics (i.e., number of observations, mean, standard deviation, median, first and third quartiles, minimum and maximum) at each assessment time point by treatment group.

Systolic blood pressure decrease event

	Statistical Analysis Plan
	Sponsor: NOVARTIS Protocol number: CRLX030A3301

A confirmed systolic blood pressure decrease event (CBPDE) is defined as systolic blood pressure decreases by > 40 mmHg from just before the study drug infusion at baseline but is ≥ 100 mmHg in 2 consecutive measurements 15 minutes apart, or if in 2 consecutive measurements 15 minutes apart, systolic blood pressure reduces to < 100 mmHg, as reported in the "Systolic blood pressure decrease event – vital signs" eCRF.

For the serelaxin arm only, the number and proportion of patients who experienced a confirmed systolic blood pressure decrease event during study drug administration will be provided. Percentages will be computed considering patients in the analysis population.

The number and proportion of patients who experienced 0, 1, 2, >2 confirmed systolic blood pressure decrease events will be provided together with the number and proportion of patients who experienced asymptomatic/symptomatic events (as recorded on the "Systolic Blood pressure Decrease Event" eCRF page).

The total number of events will be further characterized, showing absolute and relative frequencies of events for the following characteristics:

- Outcome: not recovered/not resolved, recovered/resolved, recovering/resolving, recovered/resolved with sequelae, fatal, unknown
- Action taken with study treatment: none, dose adjusted but not discontinued, permanently discontinued, dose adjusted then permanently discontinued

The category of "dose adjusted then permanently discontinued" for action taken is derived by combining the categories "dose adjusted but not discontinued" and "permanently discontinued" when recorded separately in the eCRF for the same CBPDE.

- Medications or therapies taken: yes or no, if yes type of medication/therapy (fluids/crystalloids, inotropes, vasoressors, circulatory support, mechanical ventilation, other)

Percentages will be computed considering events with non-missing information.

The number and proportion of patients who experienced at least one confirmed systolic blood pressure decrease events will be also presented by outcome, action taken and medications/therapies taken.

The number and proportion of patients who experienced at least one systolic blood pressure decrease events will be also presented by type of event in terms of SBP onset value (mmHg):

- if systolic blood pressure decreased by > 40 mmHg from baseline but was ≥ 100 mmHg;
- if systolic blood pressure reduced to < 100 mmHg.

	<h2 style="margin: 0;">Statistical Analysis Plan</h2>
	Sponsor: NOVARTIS Protocol number: CRLX030A3301

The SBP value (mmHg) at baseline (i.e., at randomization) will be summarized for patients with a confirmed SBP decrease event and for those without a confirmed SBP decrease event.

The following summaries will be presented for patients with a confirmed SBP decrease event:

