7.1 Adverse events

An AE is any untoward medical occurrence (i.e., any unfavorable and unintended sign [including abnormal laboratory findings], symptom or disease) in a subject or clinical investigation subject after providing written informed consent for participation in the study. Therefore, an AE may or may not be temporally or causally associated with the use of a medicinal (investigational) product.

The occurrence of AEs shall be sought by non-directive questioning of the patient at each visit during the study. Adverse events may also be detected when they are volunteered by the patient during or between visits or through physical examination, laboratory test, or other assessments.

Abnormal laboratory values or test results constitute AEs only if they fulfill at least one of the following criteria:

- they induce clinical signs or symptoms,
- they are considered clinically significant,
- they require therapy.

Clinically significant abnormal laboratory values or test results should be identified through a review of values outside of normal ranges/clinically notable ranges, significant changes from baseline or the previous visit, or values which are considered to be non-typical in patients with underlying disease. Investigators have the responsibility for managing the safety of the individual patient and identifying AEs. Alert ranges for lab test abnormalities are included in [Appendix 1](#).

AEs shall be recorded in the Adverse Events eCRF under the signs, symptoms or diagnosis associated with them accompanied by the following information.

- the severity grade
 - mild: usually transient in nature and generally not interfering with normal activities
 - moderate: sufficiently significant to interfere with normal activities
 - severe: prevents normal activities
- its relationship to the investigational treatment (no/yes)
- its duration (start and end dates). If the event is ongoing, an outcome of not recovered/not resolved shall be reported.
- whether it constitutes a SAE
- action taken regarding investigational treatment

- whether other medication or therapies have been taken (concomitant medication/non-drug therapy)
- its outcome (not recovered/not resolved; recovered/resolved; recovering/resolving, recovered/resolved with sequelae; fatal; unknown)

An SAE is any AE (appearance of (or worsening of any pre-existing) undesirable sign(s), symptom(s) or medical conditions(s) which meets any one of the following criteria

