9.5.2 Safety variables

All the safety analyses will be done on the Safety population.

Physical examination

As reported in [Section 6.5.1](#), significant findings that are present prior to signing informed consent will be included in the Medical History part of the eCRF: they will be summarized by treatment group by means of usual descriptive statistics for categorical variables. Significant findings after signing the informed consent, up to and including Day 5, which meet the definition of an AE or of a SAE, will be recorded on the Adverse Event section of the eCRF.

Adverse events

The incidence of Adverse Events (AEs) and Serious Adverse Events (SAEs) recorded during all the study will be presented.

For patients in SOC group, time of randomization will be considered as time of treatment initiation. Incident AEs will be considered those AEs with an onset date and time after treatment initiation. Adverse events with an onset between informed consent and treatment initiation will be listed separately. AEs will be summarized by System Organ Class and Preferred Term. Additionally, a summary of AEs by preferred term and severity using the worst reported severity grade for each event for the subject will be provided. For analysis purposes, all AEs defined as “definite”, “probable” or “possible” will be considered as related. If the relationship to study drug is unknown or missing, the AE will be considered to be drug-related. All study-drug-related AEs, AEs with an outcome of death, AEs leading to discontinuation of treatment will be summarized by percentages and frequencies. SAEs will be summarized similarly. Percentages will be based on the number of subjects in the Safety population.

Adverse Events will be further characterized and presented according to the definitions of monitored safety risks and events of interest.

Laboratory data

Summary statistics of raw data and change from screening at each assessment time point and for each laboratory parameter will be presented by treatment group. Treatment groups will be compared for changes from screening using t-tests.

Laboratory data will also be summarized by presenting shift tables for each laboratory parameter showing the number and percentage of subjects in each treatment group with the most extreme post-screening value that falls outside extended normal ranges by the classification of subjects at screening.

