4.2. SAFETY PARAMETERS

Adverse Events (AEs) / Serious Adverse events (SAEs)

All adverse events are collected through Day 5, and all serious adverse events are collected through Day 14, regardless of suspected causality. After Day 14, only suspected related serious adverse events are collected and entered in the eCRF.

Adverse events are recorded in the Adverse Events eCRF under the signs, symptoms or diagnosis associated with them, accompanied by the following information: the severity grade (mild/moderate/severe); its relationship to the study treatment (no; yes; yes, investigational treatment; yes, other study treatment (not investigational); yes, both and/or indistinguishable); its duration (start and end dates and times); whether it constitutes a serious adverse event (SAE); action taken regarding investigational treatment; whether other medication or therapies have been taken (concomitant medication or non-drug therapy); its outcome (not recovered/not resolved; recovered/resolved; recovering/resolving, recovered/resolved with sequelae; fatal; unknown).

Each pregnancy occurring to a subject involved in the trial is reported as an Adverse Event on the eCRF.

Vital signs

Height in centimeters (cm) or inches (inch) is measured at screening only.

Body weight (to the nearest 0.1 kilogram [kg] or 0.1 pound [lb] in indoor clothing, but without shoes) is measured at Screening and at 24 and 48 hours after study drug infusion in the

	Statistical Analysis Plan
	Sponsor: NOVARTIS Protocol number: CRLX030A3301

serelaxin arm / at 24 and 48 hours after randomization in SOC arm, and daily through index hospitalization, at Day 5, at discharge, and then at Day 14. These measurements during hospitalization can be performed at any time of the day.

If patient's body height/weight cannot be measured at screening because of the patient's physical condition, verbal height/weight is acceptable. Height/weight measurements shall be obtained as soon as the patient is physically able.

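### SAP 5.3 counts AEs and SAEs attributed only to non-investigational treatment as drug-related, and no planned table isolates serelaxin-attributed events

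*SAP*

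**What the plan says.** **What is collected.** SAP 4.2 describes a five-answer causality item: no, an unqualified yes, yes for the investigational treatment, and two further answers, "yes, other study treatment (not investigational); yes, both and/or indistinguishable".

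**What is tabulated.** SAP 5.3 states: "Drug-related AEs will be the AEs with relationship to study treatment equal to" any of the four affirmative answers. The third of these is "Yes, other study treatment (not-investigational". It then adds that if the "relationship to study drug is unknown or missing, the AE will be considered to be drug-related as well". Neither rule is limited to one arm. "Tables reporting general summary of AEs will be produced by treatment group", on a Safety set that includes patients who received standard of care only. "These summaries will be repeated for treatment emergent SAEs". The same section plans a detailed listing of study-drug-related AEs and gives that term no separate definition.

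**What the protocol says.** Section 7.1 has the investigator record, for each AE, "its relationship to the investigational treatment (no/yes". Section 9.5.2 treats definite, probable and possible events as related, and continues: "If the relationship to study drug is unknown or missing, the AE will be considered to be drug-related". The glossary says investigational treatment generally excludes background therapy, whereas study drug/treatment includes it.

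**The concern.** A reader of the report will take a drug-related row under the serelaxin column as the count of events that investigators attributed to serelaxin. Under SAP 5.3 it also holds events that the investigator expressly attributed to something else. An example would be hypokalemia put down to a loop diuretic and not to the infusion. Background heart failure care is required for every patient (Protocol 5.1.2), so the other-treatment answer may well be used.

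Safety and tolerability of intravenous serelaxin is a stated secondary objective, and related AEs and SAEs are among the first safety figures quoted from a report. As planned, no row answers the question Protocol 7.1 asks, although the data to answer it are collected.

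**Working it through.** The documents give no AE or causality rates, so there is no stated figure to reproduce. The check is a comparison of texts, followed by an illustration on assumed rates.

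**Comparison of texts**

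| Place | Causality assessed against | Answers counted as related |
|---|---|---|
| Protocol 7.1 | investigational treatment | yes |
| Protocol 9.5.2 | study drug | definite, probable, possible; unknown or missing |
| SAP 4.2 (eCRF) | study treatment, split by source | collection only |
| SAP 5.3 | study treatment, split collapsed | all four yes answers; unknown or missing |

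Three points follow.

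1. The SAP class is a superset. It holds every serelaxin-attributed event, plus other-treatment-only events, plus events with no causality entry.
2. The protocol's graded categories are not collected by either Protocol 7.1 or the eCRF item. SAP 5.1 says analysis follows Protocol Section 9, but that rule cannot be applied to these data.
3. The Safety set is analysed by treatment received, and SAP Table 3-2 removes patients randomized to serelaxin who received none. Nobody in the SOC column has had serelaxin, so a correctly attributed drug-related event there is either an other-treatment event or a missing entry.

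**Illustration (all rates assumed)**

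- *s*: share of serelaxin patients with a serelaxin-attributed AE.
- *b*: share of patients with an AE attributed only to other treatment.
- *m*: share of patients with an AE of missing causality.
- The three are independent, and *b* and *m* are equal in both arms.
- Arm sizes: 3,183 at 2:1 gives 2,122 and 1,061.

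Formulas under SAP 5.3:

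- Serelaxin: 1 − (1−s)(1−b)(1−m)
- SOC: 1 − (1−b)(1−m)
- Difference: s(1−b)(1−m)

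With s = 5%, b = 5%, m = 1%:

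- SOC: 1 − 0.95 × 0.99 = 0.0595, about 63 of 1,061.
- Serelaxin: 1 − 0.95 × 0.9405 = 0.1065, about 226 of 2,122.
- Difference: 0.05 × 0.9405 = 0.0470.
- Ratio: 0.1065 / 0.0595 = 1.79.
- Serelaxin-attributed share of the serelaxin column: 0.05 / 0.1065 = 47%.

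Dropping *b* but keeping missing-as-related for serelaxin-treated patients gives 1 − 0.95 × 0.99 = 5.95% (about 126 of 2,122) instead of 10.65%.

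Over s = 2–10%, b = 0–10%, m = 0–5%, the SOC column runs from 0% to 14.5% and the serelaxin column from 2% to about 23%. The serelaxin-attributed share falls from 100% to 12% (at s = 2%, b = 10%, m = 5%: 0.02 / 0.1621).

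**If *b* differs between arms** (s = 5%, m = 1%):

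- b = 5% on serelaxin, 2% on SOC: 10.65 − 2.98 = 7.67 points.
- b = 2% on serelaxin, 5% on SOC: 7.83 − 5.95 = 1.88 points.

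The difference is close to *s* only while *b* and *m* are balanced.

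**The case against.** The strongest reply is that the SAP follows the protocol's own vocabulary. The glossary puts background therapy inside study treatment, and Protocol 5.5.3.2 handles standard of care as other study treatment. On those terms the pooled class is coherent and has the same meaning in both arms. It also permits a comparison that a serelaxin-only class, zero in SOC by construction, cannot give. SAP 5.3 never calls these tables serelaxin-related. This stands. A reader might infer that the SOC column is meaningless, or that the tables fail to capture serelaxin-related events. The documents support neither reading: the events are in the table but not isolated.

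A reader might also infer that pooling dilutes the between-arm contrast. That holds for the ratio, whose reference value would otherwise be undefined (5% against 0%), but not for the risk difference under balanced attribution. Adding a flat 3 or 10 points to both arms leaves 8 − 3 = 5 and 15 − 10 = 5. The limit is that the trial is open label, so balance in attribution is an assumption.

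Counting missing causality as related is a usual conservative rule and is already in Protocol 9.5.2. It is sound for patients who received serelaxin. The weakness is only in carrying it, under a drug-related label, to patients who received none. Protocol 8.2 and 8.3 plan data checks and queries, so there is no ground for expecting many missing entries.

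The risks most open to confounding with background drugs (hypotension, hypokalemia, renal impairment) are compared by arm through MedDRA searches that do not use causality. Confirmed blood pressure decreases have separate analyses in the serelaxin arm. The split could also be recovered from the listing, but that would be done after the fact.

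These replies reduce the size of the problem. They do not explain why an event attributed only to another treatment should appear as drug-related when Protocol 7.1 asks about the investigational treatment.

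**Conclusion.** The point holds as a defect of definition and presentation worth correcting before database lock. The drug-related AE and SAE rows are a legitimate any-study-treatment class, but they depart from Protocol 7.1, and nothing planned in SAP 5.3 shows the serelaxin-attributed subset.

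The direction is certain: the serelaxin-arm percentage cannot be below the serelaxin-attributed percentage, and it exceeds it once any patient qualifies only through an other-treatment or missing answer. The size is not known. It depends on how often sites use the other-treatment answer, which turns on eCRF instructions not in these documents; that answer could be common or nearly empty. The 10.7% and 6.0% above illustrate the mechanism and are not estimates.

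The between-arm risk difference is roughly preserved if other-treatment and missing attributions are equal across arms. All-AE, all-SAE, event-of-interest and efficacy analyses do not use the flag and are unaffected.

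**What to change.** In SAP 5.3:

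- Keep the pooled row if wanted, but label it as related to any study treatment.
- Add a prespecified serelaxin-related row for patients who received serelaxin. It should comprise the investigational answer, the both-or-indistinguishable answer, the unqualified yes, and unknown or missing causality.
- Tabulate other-treatment-only attributions and missing causality separately, by arm.
- Do not impute missing causality as serelaxin-related in patients who received no serelaxin.
- Apply the same split to the SAE tables and to the listing of study-drug-related AEs.
- Reconcile Protocol 7.1, Protocol 9.5.2 (the graded categories), SAP 4.2 and SAP 5.3 on what causality is assessed against and which answers count.

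The field is already collected, so the cost is SAP wording, a derived flag and a few extra table rows.
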